12.3 Concomitant clinical management and co-interventions

Approximately 40% of women with severe early onset IUGR will develop or already have preeclampsia, this will require additional therapies, surveillance and possibly delivery indicated on maternal rather than fetal grounds.

All women with severe early onset IUGR, regardless of co-existing preeclampsia, will require intense fetal surveillance, possible in-patient stay and early delivery. Once the fetus has reached an appropriate gestational age and size (and is deemed viable) corticosteroids will be administered to improve fetal lung maturity and once delivery is planned magnesium sulphate therapy will be considered for perinatal neuroprotection. These additional therapies and management will be provided at the discretion of the clinician/study centre caring for each woman. Data regarding these co-interventions will be collected by study investigators and will be recorded in the SMD.

Sildenafil is an antihypertensive agent and may be sufficient treatment for women with hypertension. In the event that further antihypertensive treatment is required, the recommended agents are; labetalol and methyldopa. Nifedipine and other calcium channel blockers are not recommended as first line treatment but may be considered if additional treatment is required. If women are already well controlled on an agent transfer to labetalol or methyldopa is not mandatory.

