9. RANDOMISATION

This will be performed using a web-based randomisation service operating at British Columbia Women's Hospital (Vancouver, Canada). Randomisation will be stratified for;

1. Gestational age at recruitment (< or ≥ 24 weeks)
2. Present or absent/reversed end-diastolic flow in umbilical artery Doppler waveform.

Women will be randomised on a 1:1 ratio to sildenafil:placebo. The randomisation process will assign each subject with a unique study ID number. This study ID number will be required when allocating study drug containers and for recording data on the CRF. The randomisation service provides 24 hour access, 7 days per week.

If a woman is found not to be eligible for the trial when her details are entered into the randomisation program the program will return a screen failure notification. Potential subjects who have screen failed can be re-screened for eligibility and included in the trial at a later date if appropriate.

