10. TREATMENT GROUPS & STUDY DRUG

10.1 Treatment groups

Women will be randomised to one of two groups:

1. *Sildenafil*
Oral sildenafil citrate 25mg three times daily (tds).

OR

2. *Placebo*
Matching placebo tablets containing no active ingredient three times daily (tds).

Participants, medical professionals caring for women and study investigators will remain blinded to treatment allocation until the study is completed and database lock has occurred.

These dosing regimens have been set in line with the STRIDER IPD Collaboration.

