10.4 Emergency Unblinding

In the event that there is an immediate need for the treating doctor to know a subject's treatment allocation in order to ensure patient safety it will be possible to break the randomisation code. The facility to perform emergency unblinding will be available 24 hours per day. It is recommended that the Investigator contact the Auckland Principal Investigator to discuss the particular situation before breaking the subject's randomisation code, if possible.

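### The hypertension guidance in Section 12.3 is worded as if every woman were taking sildenafil, although half receive blinded placebo (minor patient-safety wording error)

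*Protocol*

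**What the plan says.** Section 12.3 of the protocol tells sites how to handle concomitant conditions during the trial. On hypertension it says: "Sildenafil is an antihypertensive agent and may be sufficient treatment for women with hypertension". It continues: "In the event that further antihypertensive treatment is required, the recommended agents are; labetalol and methyldopa". Calcium channel blockers are discouraged as first choice but allowed as an addition, and then: "If women are already well controlled on an agent transfer to labetalol or methyldopa is not mandatory". The same section expects hypertensive disease to be common: "Approximately 40% of women with severe early onset IUGR will develop or already have preeclampsia".

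On allocation, Section 9 says: "Women will be randomised on a 1:1 ratio to sildenafil:placebo". Section 10.1 describes the control tablets as matching and without active ingredient, and adds, up to completion and database lock: "Participants, medical professionals caring for women and study investigators will remain blinded to treatment allocation". Section 10.4 provides round-the-clock emergency unblinding, on the condition "In the event that there is an immediate need for the treating doctor to know" the allocation for the woman's safety. Section 15 likewise speaks of urgent clinical need.

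**The concern.** As pharmacology, the first sentence is a hedged remark about a drug. Its place in the protocol makes it guidance for managing randomised women. Saying that sildenafil may suffice, and then calling labetalol or methyldopa *further* treatment, makes sense only if the woman is already receiving sildenafil. For a woman on placebo that is untrue, and her clinician does not know it.

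What is at stake is maternal care, not inference. A clinician could take the text as a reason to count inactive tablets as antihypertensive treatment and so lean towards treating less. No bias in the trial's comparisons is claimed.

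**Working it through.** No calculation decides this point. It rests on reading the sections together.

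1. **Which sildenafil is meant?** Section 8 says that women who decline the trial will not get sildenafil as part of usual care. In guidance for trial participants, the sildenafil that might suffice can therefore only be the study tablet.

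2. **Is the premise true for each participant?** Sections 9 and 10.1 give each woman a 1 in 2 chance of tablets with no active ingredient. The premise fails for about half.

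3. **Can the clinician tell which half?** Not in routine care. Section 10.1 blinds those looking after the women. Unblinding under Sections 10.4 and 15 is reserved for immediate or urgent need, so it is not a tool for ordinary blood pressure decisions.

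4. **Is it corrected elsewhere?** No. Section 12.3 does not mention placebo, and no other section tells sites to disregard the tablets when judging whether blood pressure is treated. Section 11.2 also ranks the study drug among antihypertensives when it refers to *other* such drugs. There the assumption concerns hypotension and errs on the safe side; in Section 12.3 it points towards less treatment. Section 11.1 uses the neutral term *study drug*, so neutral wording was available.

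**Scale, for illustration only**

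- Total sample size (Section 7.1): 58 per group gives 2 × 58 = 116; adding 5% gives 116 × 1.05 = 121.8, the stated 122.
- Placebo arm under 1:1 allocation: 122 / 2 = 61.
- Preeclampsia proportion (Section 12.3): about 40%.
- Placebo women to whom the text might be applied: 61 × 0.40 = 24.4, about 24.

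This count is imperfect in both directions. It omits hypertension without preeclampsia (Section 13.1 lists gestational hypertension separately), for which the protocol gives no rate. It includes women already controlled on another agent.

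**Scheduled blood pressure checks** (Section 12.2: 48 hours, days 5, 10 and 14, then weekly). The gaps are 2 − 0 = 2, 5 − 2 = 3, 10 − 5 = 5, 14 − 10 = 4, then 7 days. The same section expects clinical assessments to be more frequent than this in many cases.

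**The case against.** The strongest reply is that the operative instruction does not depend on allocation. Labetalol or methyldopa is given when treatment is needed, and a placebo woman whose pressure stays high meets that condition like anyone else. The disputed sentence says only *may*. It imposes no wait, raises no threshold and withholds no drug. Section 12.3 also says that preeclampsia will call for additional therapies, whatever the arm, which weakens the count of 24 because that count consists of preeclampsia cases. The protocol names sildenafil elsewhere in text that covers all blinded women, such as contraindications (Section 6.2) and side effects (Section 4.3), without implying that everyone takes it. Section 11.2 already deals with severe hypotension by stopping other antihypertensives first. Finally, the women are under Maternal Fetal Medicine high-risk teams (Section 8), with surveillance for preeclampsia described as essential (Section 4.2), and those teams know that the trial has a placebo arm.

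Most of this stands as a limit on harm, and it is why the point is minor. The count of 24 should carry no weight beyond showing that the situation will arise. The reply does not make the premise true for placebo women. The comparison with contraindications and side effects also falls short: assuming sildenafil there is precautionary, whereas assuming it when judging whether hypertension is treated is not. The remark on additional therapies is general and does not tell sites to leave the study tablets out of account.

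**Conclusion.** The concern holds as a minor patient-safety wording error. Guidance for blinded participants rests on an assumption that is wrong for about half of them and that the clinician cannot check in routine care. The risk is small, given the permissive wording, the need-based trigger for other agents, investigator discretion, specialist care and frequent checks. No document evidence shows that treatment would in fact be delayed; that is an inference about how the text could be read. The illustrative 24 assumes equal arms of 61 and that the 40% figure applies equally to the placebo arm. Sample size, endpoint, analysis and blinding are untouched. It is still worth correcting, because the statement sits in operative guidance and the correction costs almost nothing.

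**What to change.** Replace the first of the two sentences in Section 12.3 with: *Treat hypertension on measured blood pressure by usual clinical criteria, without assuming that the study drug is active; watch for an additive hypotensive effect in case the woman is receiving sildenafil.* Delete the word *further* from the sentence that follows. Keep the rest of the paragraph, including the advice on calcium channel blockers and on women already well controlled.

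The warning about additive hypotension overlaps in part with the stopping rule in Section 11.2, but it keeps the legitimate pharmacological caution beside the advice on choice of agent. The cost is two reworded sentences in an amendment and a note to sites.

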12.4 Placental tissue (for Auckland study recruits only)

A biopsy of placental tissue will be taken after delivery. This tissue will be analysed within the laboratory to compare the effect of sildenafil and placebo on chorionic plate and stem villous blood vessels within the placenta. See appendix for sample collection details.

This part of the study will be optional and women will have the opportunity to take part in the STRIDER NZAus study without consent for placental examination if they wish.

12.5 Myometrial biopsy: (for Auckland study recruits only)

The majority of women will require delivery by caesarean section (CS) due to the high risk nature of their pregnancy and risk to the fetus/neonate going through the stress of labour. In women undergoing CS, a small piece of muscle (approximately 0.5cm x 0.5 cm x 0.5cm) will be dissected from the uterine wall (at the site of the placental attachment) at the time of delivery in women undergoing caesarean section. The technique for sampling is safe and has been used for many years for research purposes; it will not affect the duration of the operation, cause any pain or discomfort to women and will not impair uterine healing following surgery. See appendix for sample collection details.

This part of the study will be optional and women will have the opportunity to take part in the STRIDER NZAus study without consent for myometrial examination if they wish.

12.6 Outcome data collection

Detailed data will be collected regarding delivery, maternal and fetal outcomes from the maternal and neonatal records. Maternal outcome data will be collected until the time of maternal hospital discharge. Neonatal outcome data will be collected to the time of hospital discharge or EDD, whichever is later. For neonates who are discharged from hospital prior to their EDD a phone call will be conducted by the Investigator or site

staff, i.e. research midwife, to collect any additional data/confirm no new diagnoses have been made up to the date of EDD.

A maternal and neonatal post-partum questionnaire will be carried out 6 – 12 weeks after delivery and will include request for agreement to follow up paediatric outcomes at 18-36 months (subject to additional funding being obtained).

13. SAFETY ASSESSMENT & MONITORING

13.1 Assessment of Adverse Events

Information will be collected regarding all adverse events (AE) that occur from the time of randomisation until maternal hospital discharge after delivery; fetal/neonatal death occurring prior to discharge or EDD; neonatal hospital discharge or EDD, whichever is later.

The general definition of an AE is any unfavourable and unintended change in structure, function, or chemistry of the body temporally associated with the study medication whether or not considered related to the use of the study medication. Worsening of pre-existing condition which is temporally associated with the use of the study medication may also be considered an AE.

In this high-risk population a large number of complications are anticipated in the absence of trial participation. Investigators should take the underlying condition into account in their assessment of potential adverse and serious adverse events. In general the following expected events do not need to be reported as AEs/SAEs unless the Investigator considers the event to be possibly, probably or definitely related to the study drug; these events will be documented in the CRF as part of maternal, delivery and neonatal outcomes:

- Gestational hypertension
- Preeclampsia
- Preterm delivery
- Hospitalisation due to preeclampsia
- Hospitalisation for fetal monitoring due to IUGR
- Hospitalisation for delivery
- Caesarean section
- Postpartum haemorrhage >500ml and <1000ml
- Admission to NICU
- Neonatal complications of prematurity

13.2 Serious Adverse Events

In this trial the following will be considered serious adverse events:

- Maternal death
- Fetal death
- Neonatal death

- Maternal life threatening event
- Maternal persistent or significant disability or incapacity
- Major antepartum or postpartum haemorrhage (>1000ml)
- Maternal hospitalisation/prolonged hospitalisation not related to preeclampsia, IUGR or standard postnatal recovery
- Unexpected congenital anomaly/birth defect
- Other medically important event considered to be an SAE by Investigator

Important medical events that may not result in death, threat to life, or not require hospitalisation may be also considered a serious AE when, based upon appropriate medical judgment, the event may jeopardize the subject and may require medical or surgical intervention to prevent one of the outcomes listed above. The term life threatening here refers to an event in which the patient is at risk of death at the time of the event; it does not refer to an event that might hypothetically cause death if it was more severe.

13.3 Investigator review of AEs/SAEs:

The maximum intensity of adverse and serious adverse events must be assessed by an Investigator. The following are the minimum parameters to be collected for each event:

- Maximum intensity:
 - Mild is awareness of sign or symptom, but easily tolerated
 - Moderate is discomfort enough to interfere with usual activity
 - Severe is incapacitating with inability to work or do usual activity
 - Death
- Duration. The start and stop dates will be identified and recorded.
- Action taken in regards to the study drug. Does the event cause the study medication to be temporarily or permanently discontinued?
- Relationship to study medication. The investigator will determine if the study medication contributed to the AE/SAE. Factors to consider:
 - Exposure: Was subject exposed to the study drug?
 - Likely cause: Is the event reasonably explained by aetiology such as underlying disease or other environmental factors?
 - Re-challenge: Was the subject re-exposed to the study drug? If yes, did the event recur or worsen?

Consistency with the study medication: Is the clinical/pathology presentation of the event consistent with previous knowledge regarding the study medication?

- Details of any treatment given.

Expectedness of SAEs

SAEs must also be assessed for expectedness in this clinical setting. The Investigator is responsible for determining whether an SAE is expected or not based on the underlying severe IUGR and the published reference safety information for sildenafil (this can include a sildenafil Investigator's Brochure, MedSafe/TGA product Data Sheets and this protocol). An unexpected adverse event/reaction is one that is not reported in the reference safety information, is more severe than previously reported or is not reasonably explained by the underlying condition.

Review of all of the known information about the SAE should conclude one of the following:

Expected Events:

- Expected Unrelated Event: the SAE is expected based on the known information about the study drug or the underlying condition and is not considered to be related to the study drug. This is referred to as an Expected SAE.
- Expected Related Event: an SAE which the Investigator considers possibly, probably or definitely related to the study drug. This is referred to as a SAR – Serious Adverse Reaction.

Unexpected Events:

- Unexpected Unrelated Event: the SAE is unexpected based on the known information about the drug or the underlying condition and is not considered related to the study drug. This is referred to as an Unexpected SAE.
- Unexpected Related Event: the SAE is unexpected based on the known information about the drug or the underlying condition and is considered possibly, probably or definitely related to the study drug. This is referred to as a SUSAR – Suspected Unexpected Serious Adverse Reaction.

In this cohort of early-onset severe IUGR and with the lack of an alternative therapy, fetal or neonatal death due to complications of severe IUGR or prematurity and prolonged stay in the neonatal unit and may occur and in this setting and so may be Expected Events (Expected SAEs). These fetal or neonatal deaths in the study reporting period will be recorded as SAEs on the CRF but do not require immediate reporting unless the Investigator has specific concerns about these events or believes they are likely to be causally related to the study drug i.e. considered as a SAR or SUSAR.

Maternal death and maternal life-threatening complications should always be considered unexpected events in this population and require immediate reporting.

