4.3 Potential Risks of Sildenafil Treatment

The most common sildenafil related side effects are headache, flushing, dyspepsia, nasal congestion and impaired vision, including photophobia and blurred vision. (Sildenafil Citrate Data Sheet. Actavis. www.medsafe.govt.nz/profs/datasheet/s/silagratab.pdf). None of the women treated with sildenafil for severe early onset IUGR at British Columbia Women's Hospital complained of side effects [11] and sildenafil was similarly well tolerated in the UK RCT for pre-eclampsia [10]. Women will be asked to verbally report side effects and record these in their Subject Medication Diary (SMD) and this data will be collected in the CRF.

It is possible that sildenafil may improve fetal growth velocity to gain gestational age and maturity to a level that an infant that would have demised in-utero actually survives but due to the nature of extreme preterm birth and growth restriction has significant long term handicap. However if sildenafil does demonstrate an improvement in fetal growth velocity that results in improved survival, it is likely that it will also improve fetal growth in babies that would usually have survived with handicap to allow them to reach an age and size where handicap is less likely. One of the primary aims of this study is to assess this potential impact.

It is also possible that sildenafil has no effect or a negative effect on fetal growth velocity. In addition, vasodilatation in an already compromised fetus (with abnormal fetal Doppler waveforms) may lead to decompensation and earlier demise of a sick fetus. These possibilities can only be accurately assessed through an RCT of this nature.

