13.4 Procedure for AE and SAE Reporting

All AEs and SAEs must be documented in the subject's CRF. SAEs may also require immediate reporting by the site, as below:

Actions for SAEs:

1. Report immediately, within 24 hours of becoming aware of the event:
 - SAR – suspected adverse reaction.
 - Unexpected SAE.
 - SUSAR – Suspected Unexpected Serious Adverse Reaction.

2. Documented in the CRF only (do not require immediate reporting):
 - Expected SAE.

Unexpected SAEs, SUSARs and SARs will be reported to the STRIDER DSMB, regulatory authorities and ethics committees, as required.

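### The causality threshold that sends a fetal or neonatal death to 24-hour reporting is worded inconsistently: the SAR and SUSAR definitions start at *possibly* related, the paragraph on deaths says *likely*

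*Protocol*

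**What the plan says.** Section 13.2 lists fetal death and "Neonatal death" among the serious adverse events. The expectedness part of section 13.3 then sorts serious events by expectedness and relatedness:

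- An expected, related event is "an SAE which the Investigator considers possibly, probably or definitely related to the study drug"; this is a SAR.
- An unexpected event becomes a SUSAR when it "is considered possibly, probably or definitely related to the study drug".
- An expected, unrelated event is one that "is not considered to be related to the study drug. This is referred to as an Expected SAE".

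Section 13.4 fixes the action. For SARs, SUSARs and Unexpected SAEs the instruction is "Report immediately, within 24 hours of becoming aware of the event". Only Expected SAEs are left to the CRF alone. The same three reportable classes go on to the DSMB, regulators and ethics committees as required; Expected SAEs are not in that list.

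Between the definitions and the action list, 13.3 has a paragraph specific to this population. It says that "fetal or neonatal death due to complications of severe IUGR or prematurity" may count as an expected event. Such deaths are entered on the CRF as SAEs but need no immediate report, with two exceptions: the investigator has particular concerns about the death, or "believes they are likely to be causally related to the study drug i.e. considered as a SAR or SUSAR".

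**The concern.** The death paragraph attaches the labels SAR and SUSAR to a belief that the drug is a *likely* cause. A few lines earlier the same labels begin at *possibly*. A death graded *possibly* related therefore meets the definition, but it does not meet the literal wording of the causality exception written for deaths.

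The parallel waiver in section 13.1 sharpens the contrast. For lesser expected events, such as caesarean section or NICU admission, the waiver lapses at *possibly, probably or definitely* related. Read literally, the causality trigger for a death is higher than the one for a NICU admission, and the protocol gives no reason.

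The wording bears on a harm the protocol itself foresees: section 4.3 warns that vasodilatation in a compromised fetus "may lead to decompensation and earlier demise of a sick fetus". Investigators are blinded (section 10.1) and are asked in 13.3 to weigh whether the underlying disease explains an event, so *possibly* is a plausible grade for such a death. If it were filed as CRF-only, it would also miss the onward route in 13.4.

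**Working it through.** No arithmetic applies. The check follows one case, a fetal or neonatal death in a growth-restricted pregnancy, through the text for each relationship grade.

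**Inputs.** Seriousness comes from 13.2. The SAR, SUSAR and Expected SAE definitions and the death paragraph come from 13.3. The action list comes from 13.4.

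**Three ways to route the death**

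1. *Definitions plus action list.* Any grade from *possibly* upward makes the death a SAR if expected or a SUSAR if unexpected. 13.4 then requires a report in 24 hours.
2. *Death paragraph, with* likely *taken at face value.* A death believed to be a likely drug effect is reported at once. A death graded only *possibly* related is CRF-only, unless the investigator has particular concerns.
3. *Death paragraph, with its closing words resolved through the definitions.* Being considered a SAR or SUSAR starts at *possibly*, so the death is reported in 24 hours.

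**Result by grade**

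| Grade | Route 1 | Route 2 | Route 3 |
|---|---|---|---|
| Not related, expected | CRF only* | CRF only* | CRF only* |
| Possibly | 24 hours | CRF only* | 24 hours |
| Probably or definitely | 24 hours | 24 hours | 24 hours |

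*Under the death paragraph, particular concerns on the investigator's part would still bring an immediate report.

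The routes disagree in one cell: a death graded *possibly* related, handled by route 2. Routes 1 and 3 agree throughout. *Likely* is not one of the three grades in 13.1 and 13.3, so a site has to translate it. The table takes it as equivalent to *probably* or above, which is its ordinary meaning.

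**The case against.** The strongest reply is that the protocol, read as a whole, already requires these deaths to be reported.

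- The disputed clause ends by naming SAR and SUSAR, both defined just above, so *likely* can be taken as loose drafting that defers to the definitions.
- The paragraph concerns deaths that may be Expected SAEs, and an Expected SAE is by definition unrelated. A death judged possibly related is not one.
- The 13.4 list is unambiguous and reserves CRF-only handling for Expected SAEs.
- The separate trigger of particular concerns would plausibly be met by anyone who suspects the drug.

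Most of this stands, and it rules out a stronger reading that a reader might infer: that the protocol outright exempts possibly related deaths. What survives is narrower. The paragraph is specific to deaths and supplies its own relatedness test for leaving the waiver. If it covered only unrelated deaths, that test would be unnecessary. The concerns trigger is undefined and discretionary, whereas the definitions make reporting mandatory from *possibly* upward.

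A reader might also want a number. In Table 1, (17 − 6) + (10 − 5) = 16 of 27 did not survive, or 59%. Applied to 122 women this gives about 72 deaths, of which some share would be graded *possibly*. The documents do not support that step. The series is small and non-randomised. Median gestation at eligibility in its untreated group was 148 days, against this trial's lower limit of 22 × 7 = 154 days, so at least half of the group that contributes 11 of the 16 losses lay below the limit. The share graded *possibly*, and the share of sites reading the paragraph literally, would be pure assumption.

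Nor do the documents show that a safety signal would be delayed. Every such death is recorded on the CRF with its relationship to study drug, section 18 puts SAEs in monthly progress reports to investigators, and section 13.5 does not say which deaths the DSMB reviews or when.

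**Conclusion.** The inconsistency is real and confined to one grade: a fetal or neonatal death judged *possibly* related. The definitions and 13.4 require a report within 24 hours. The death paragraph can be read either way, with the better reading in favour of reporting.

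This is a drafting fault in a safety procedure. It is not a gap in the classification scheme, and it is not evidence that deaths have been or will be withheld. The number of deaths affected cannot be derived from the documents.

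The conclusion rests on two assumptions: that *likely* is understood in its ordinary sense, above *possibly*, and that a site handling a death may turn to the paragraph written for deaths before the general definitions. The point should be acted on because the correction is nearly free and because the event is a harm that 4.3 raises as a possible drug effect.

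**What to change.** In the death paragraph of 13.3, replace the *likely* test with the grades the protocol already uses in 13.1 and in the definitions: *possibly, probably or definitely* related. Keep the cross-reference to SAR and SUSAR and the separate trigger for particular concerns. Every death that meets either definition then follows the 13.4 route on any reading.

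Tell sites of the change in a short memo. Check any death already filed CRF-only: where the recorded relationship is *possibly* or higher, send it by the 13.4 route. This is a check of the reporting route and needs no new causality grading.

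The same amendment could correct the expansion of SAR in 13.4, which reads as a suspected reaction where 13.3 and the abbreviation list have a serious one.

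The cost is a few words, one memo and a file check. The downside is possibly a few more expedited reports. Treatment, sample size and analysis are unaffected.
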